9.2. Clinical Laboratory Evaluations

All safety laboratory evaluations will be done at local laboratories. Blood and urine samples for laboratory analysis are collected at Screening, on Day 1 and Day 8 of each cycle for balixafortide + eribulin, on Day 2 and Day 9 of each cycle for eribulin monotherapy, and at the end of treatment visit. The results of Day 1 for balixafortide + eribulin and Day 1 and Day 2 for eribulin monotherapy will be presented together. The results of Day 8 for balixafortide + eribulin and Day 8 and Day 9 for eribulin monotherapy will be presented together.

For hematology and biochemistry, absolute values and changes from baseline will be summarized by study treatment arm and cycle/day number. Change from baseline will be calculated as (value at a treatment cycle/day value at baseline).

For those parameters where NCI CTCAE v5.0 grades are derivable, shift tables from baseline to each post-baseline time point will be presented by NCI CTCAE v5.0 grades. For all the other parameters, shift tables will be presented by analysis range (normal, high or low). For any shift table, percentages will be calculated using available data per cycle/day number for each laboratory parameter.

All safety laboratory test results will be summarized by study treatment arm, overall, by cycle and by day and also presented in data listings. Coagulation parameters (International Normalized Ratio [INR] and prothrombin time) will be listed only. Boxplots of mean \pm standard error at each cycle/day number will be created for each parameter.

Urinalysis data will be listed only.

9.2.1. Hematology

The following parameters will be assessed: white blood cell (WBC) count with differential, red blood cell (RBC) count, hemoglobin (Hb), hematocrit (Ht), platelet count, Neutrophils, Lymphocytes, Eosinophils, Monocytes and Basophils.

9.2.2. Biochemistry

The following parameters will be assessed: albumin, total protein, alanine aminotransferase (ALT), aspartate transaminase (AST), total bilirubin (TBL), direct bilirubin, indirect bilirubin, gamma-glutamyl transferase (GGT), alkaline phosphatase (ALP), glucose, creatinine, blood urea nitrogen (BUN), urea, creatine kinase (CK), calcium (Ca), potassium (K), sodium (Na), and magnesium (Mg).

Potential cases of drug induced liver injury will be listed and summarized by treatment arm. Potential cases of drug induced liver injury are defined using concurrent ALT, AST and TBL as follows:

- For patients with all 3 parameters (ALT, AST and TBL) within the normal range at baseline:
 - ALT or AST \geq 3 times the upper limit of normal (x ULN) with TBL \geq 2 x ULN with no evidence of hemolysis and an ALP value \leq 2x ULN or not available.;
- For patients with pre-existing ALT or AST values above the ULN at baseline:

- (ALT or AST) ≥ 2 x baseline and (ALT or AST) ≥ 3 x ULN and TBL ≥ 2 x ULN. Note that the double criterion on (ALT or AST) requires values \ge maximum value of 2 x baseline and 3 x ULN which ensures an increase from baseline even in the case of a very large baseline value >3 x ULN;
- As above with additional more stringent criterion of (ALT or AST) $\geq 8 \times ULN$.
- For patients with pre-existing values of total bilirubin above the normal range at baseline:
 - (ALT or AST) \geq 3 x ULN and (TBL>= baseline + ULN and TBL \geq 3 x ULN);
 - As above with additional more stringent criterion of (ALT or AST) $\ge 8 \times ULN$.

A log-log plot of maximum ALT/AST/ALP vs maximum total bilirubin will be created to identify potential cases of concern. Additionally, an individual profile over time for each ULN-normalized liver function test (ALT, ALP, AST and TBL) will be plotted for all the potential cases.

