9.2.6 Monitoring and Management of AESIs and AEPIs

9.2.6.1 Potential Cases of Drug-induced Liver Injury

Abnormal values in AST and/or ALT levels concurrent with abnormal elevations in total bilirubin level that meet the criteria outlined below in the absence of other causes of liver injury are considered potential cases of drug-induced liver injury (potential Hy's Law cases) and should always be considered important medical events.

- Patients with baseline AST or ALT and total bilirubin values within the normal range who subsequently present with AST or ALT values ≥3x ULN concurrent with a total bilirubin value ≥2x ULN with no evidence of hemolysis and an alkaline phosphatase (ALP) value ≤2x ULN or not available.
- For patients with pre-existing ALT or AST or total bilirubin values above the ULN, the following threshold values should be used in the definition mentioned above:
 - For patients with pre-existing baseline AST or ALT values above the normal range: AST or ALT values ≥2x the baseline values and ≥3x ULN, or ≥8x ULN (whichever is smaller).
- For patients with pre-existing values of total bilirubin above the normal range:

Protocol No.: POL6326-009

Version 3.0

 Total bilirubin level increased from baseline by an amount of at least 1x ULN or if the value reaches ≥3x ULN (whichever is smaller).

In addition to repeating measurements of AST and ALT, laboratory tests should include albumin, creatine kinase (CK), total bilirubin, direct and indirect bilirubin, gamma-glutamyl transferase (GGT), prothrombin time/international normalized ratio (INR), and ALP. A detailed history, including relevant information, such as review of ethanol, acetaminophen, recreational drug and supplement consumption, family history, occupational exposure, sexual history, travel history, history of contact with a jaundiced person, surgery, blood transfusion, history of liver or allergic disease, and work exposure, should be collected.

Further testing for acute hepatitis A, B, or C infection and liver imaging (e.g., biliary tract) may be warranted. All cases confirmed on repeat testing as meeting the laboratory criteria defined above, with no other cause for liver function test (LFT) abnormalities identified at the time should be considered potential Hy's Law cases irrespective of availability of all the results of the investigations performed to determine etiology of the abnormal LFTs. Such potential Hy's Law cases must be reported as SAEs (see Section 9.2.5.1).

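### SAP 9.2.2 applies the larger, not the smaller, of two bilirubin limits when baseline bilirubin is raised, so its liver-injury cases differ from those of protocol 9.2.6.1

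*SAP*

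**What the plan says.** Both documents start from the same rule for patients with normal liver tests at baseline: ALT or AST at least 3x ULN, with concurrent bilirubin at least 2x ULN, no hemolysis, and ALP at most 2x ULN or not available. They part for abnormal baselines.

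**Protocol 9.2.6.1.** For patients with raised baseline values, the protocol replaces the thresholds only; the new "threshold values should be used in the definition mentioned above". For raised bilirubin: "Total bilirubin level increased from baseline by an amount of at least 1x ULN or if the value reaches ≥3x ULN (whichever is smaller". For raised ALT/AST: "AST or ALT values ≥2x the baseline values and ≥3x ULN, or ≥8x ULN (whichever is smaller". The protocol then adds a further step. "All cases confirmed on repeat testing as meeting the laboratory criteria defined above", with no other cause identified at the time, count as potential Hy's Law cases and are reported as SAEs.

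**SAP 9.2.2.** For raised bilirubin, the SAP requires ALT or AST at least 3x ULN together with "TBL>= baseline + ULN and TBL \geq 3 x ULN". For raised ALT/AST, it requires at least 2x baseline and at least 3x ULN, with bilirubin at least 2x ULN, and explains that this is a double criterion "which ensures an increase from baseline even in the case of a very large baseline value". The 8x ULN figure appears as a second tier in each abnormal-baseline group: "As above with additional more stringent criterion of (ALT or AST". The wording "with no evidence of hemolysis and an ALP value" (at most 2x ULN or not available) appears only in the all-normal group.

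**The concern.** Joining two lower limits with 'and' makes the larger one bind; 'whichever is smaller' makes the smaller one bind. For raised baseline bilirubin the two documents therefore set opposite rules from the same pair of numbers, and the SAP gives no reason. Its one explanatory note concerns ALT/AST.

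Three further differences sit beside this one:

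- **ALP and hemolysis.** These conditions are missing from the SAP's abnormal-baseline groups.
- **Raised on both.** The SAP's two abnormal-baseline groups overlap, and nothing says how a patient in both is classified.
- **8x ULN.** The protocol's alternative route for ALT/AST becomes an additional requirement in the SAP.

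At stake is the match between the SAP's case listing and by-arm summary and the laboratory cases the protocol defines. These may be small counts, where one patient moved in or out can change how the arms compare.

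**Working it through.** Neither document states a figure to reproduce, so the check codes both rules and compares them. All values are multiples of ULN; b is the patient's baseline.

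**Inputs.** The thresholds are those set out above. The eligible range comes from protocol 5.1, criterion 10e: bilirubin at most 1.5; ALT/AST at most 3, or 5 with liver metastases. That cap applies at Screening. SAP section 4 takes the last pre-dose value as the safety baseline, so a baseline above the cap is possible.

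**1. Bilirubin raised, ALT/AST normal.** Protocol limit = min(b + 1, 3). SAP limit = max(b + 1, 3).

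| Baseline | Protocol | SAP | Gap |
|---|---|---|---|
| 1.05 | 2.05 | 3.0 | 0.95 |
| 1.2 | 2.2 | 3.0 | 0.8 |
| 1.5 | 2.5 | 3.0 | 0.5 |
| 2.0 | 3.0 | 3.0 | 0 |
| 2.2 | 3.0 | 3.2 | 0.2 |

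Below baseline 2.0 the gap is 3 − (b + 1) = 2 − b. The rules agree only at 2.0, which lies above the Screening cap.

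**2. ALT/AST raised, bilirubin normal.** Protocol ALT/AST limit = min(max(2b, 3), 8). SAP first-tier limit = max(2b, 3). They are identical up to b = 4. Beyond that, protocol against SAP is 8 against 8.5 at 4.25, 8 against 9 at 4.5, and 8 against 10 at 5.

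**3. Raised on both.** Under the protocol both raised thresholds replace those in the main definition. Read literally, the SAP lets such a patient qualify through either group.

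- Through the ALT/AST group, the SAP bilirubin limit is 2.0 against the protocol's b + 1. The SAP is looser by b − 1, which is 0.5 at b = 1.5.
- Through the bilirubin group, the SAP ALT/AST limit is 3.0 against the protocol's 4, 5, 6 and 8 at ALT/AST baselines 2, 2.5, 3 and 4. There is no difference up to 1.5.

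**4. Illustrative patients.** No hemolysis; ALP 1.5 unless stated.

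| Baseline ALT / bilirubin | On study ALT / bilirubin | Protocol | SAP | Reason |
|---|---|---|---|---|
| 0.8 / 0.9 | 6 / 2.6 | case | case | both limits 2.0 |
| 0.8 / 1.2 | 6 / 2.6 | case | not a case | limit 2.2 against 3.0 |
| 4.5 / 0.9 | 8.5 / 2.2 | case | not a case | ALT limit 8 against 9 |
| 1.5 / 0.9 | 4 / 2.2, ALP 3 | not a case | case | ALP condition absent from SAP group |
| 1.5 / 1.2 | 6 / 2.1 | not a case | case | bilirubin limit 2.2 against 2.0 |
| 2.5 / 1.2 | 3.2 / 3.1 | not a case | case | ALT limit 5 against 3 |

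The mismatch runs in both directions. The last two rows depend on the either-group reading of the SAP.

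**The case against.** Protocol 9.2.6.1 is a monitoring and reporting rule for sites, not an analysis specification. The protocol's planned liver evaluation is the log-log plot and time-course plots of section 4.4.3, and section 12.4.2 plans no listing of these cases. On that view the SAP listing is an added output that need not reproduce 9.2.6.1, and the absence of an entry in SAP section 12 is weak evidence of an undeclared change. The section 12 argument is fair and is not relied on here. The conflict remains: both documents use the same case label and the same building blocks, so a reader of the by-arm summary would take it to count the protocol's laboratory cases.

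The protocol too sets a higher bilirubin limit for raised baselines than the 2.0x ULN used for normal ones, so a higher limit is not in itself an anomaly. That stands. The difference is in form: the protocol limit rises gradually (2.05 at baseline 1.05), while the SAP limit jumps to 3.0 as soon as baseline passes normal.

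On the secondary points:

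- The SAP's note suggests its ALT/AST double criterion was intended, and the resulting difference matters only above 4x ULN at baseline. Both are accepted.
- Omitting the ALP and hemolysis conditions widens the screen and hides nobody. That is correct, but it still adds cases the protocol excludes.
- The raised-on-both results assume an unstated SAP rule, and the protocol does not expressly say how its two thresholds combine. Applying both is the natural reading of substituting thresholds within one definition, but these results are less firm than the bilirubin finding.

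Finally, there are safeguards. SAE tables, laboratory listings, shift tables, the log-log plot and the investigator-identified hepatic AEPI do not use this rule. They limit the consequence, but they do not correct the listing or its summary.

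**Conclusion.** The concern holds. For every raised bilirubin baseline that eligibility allows at Screening, with normal ALT/AST, the SAP limit exceeds the protocol's by between 0.5x ULN and just under 1.0x ULN, and patients in that band are protocol cases but not SAP cases. This rests only on 'and' against 'whichever is smaller'. The missing ALP and hemolysis conditions and the 8x ULN difference also follow from the text, the latter for a narrow group. The raised-on-both differences depend on reading the SAP groups as alternatives.

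The reach is one safety listing and its by-arm summary; no efficacy result or alpha allocation is touched. The documents give no frequency of abnormal baselines, so neither the number of patients nor the net direction can be computed, and the counts could coincide. It should be fixed because the SAP as written contradicts the protocol's own case definition. Which threshold is clinically right is not judged here.

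**What to change.** Reconcile SAP 9.2.2 with protocol 9.2.6.1 in one of two ways:

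1. Program the SAP screen to the protocol text: the smaller-of-two bilirubin rule, 8x ULN as an alternative for raised ALT/AST, and the ALP and hemolysis conditions in every baseline group.
2. Keep the SAP rule, and state and justify the difference.

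In either case, state how a patient raised on both ALT/AST and bilirubin is classified. Label the output a laboratory screen, since the protocol also asks for confirmation on repeat testing and no other identified cause.

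The threshold and ALP changes are a small text and programming edit. Hemolysis needs a stated derivation or case review: neither document gives a rule, and the laboratory list in protocol 9.9 names no hemolysis-specific test. Some patients may enter the listing and others may leave it.

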9.2.3. Urinalysis

The following parameters will be assessed: appearance, color, dipstick (pH, Specific gravity, ketones, protein, glucose, blood, bilirubin, nitrite, leukocytes, bacteria, casts, crystals, epithelial cells, red blood cells, white blood cells and other results). Microscopic analysis if warranted by Dipstick results. Bacteria, casts, crystals, epithelial cells, red blood cells, white blood cells and other results, red blood cells, white blood cells and other results.

9.3. Vital Sign Measurements

Weight, BSA, body temperature and resting blood pressure and respiratory and pulse rate will be measured in all patients at Screening, and at the EoT visit.

Weight and vital signs will also be assessed on Day 1 of each cycle for patients on the balixafortide + eribulin treatment arm and on Day 2 of each cycle for patients on the eribulin monotherapy treatment arm.

The vital sign results and changes from baseline will be summarized by cycle and treatment arm. A data listing will be produced as well.

9.4. Physical Examination

Physical examination will be performed at Screening, on Day 1 of each cycle for patients on the balixafortide + eribulin treatment arm and on Day 2 of each cycle for patients on the eribulin monotherapy treatment arm and in all patients at the EoT visit.

A summary table for the shift from baseline to post-baseline timepoints for physical exam will be presented by treatment arm. All physical examination results will be presented in a data listing.

9.5. Electrocardiogram

An electrocardiogram (ECG) will be performed at the clinical site during the visits and timepoints shown below.

Treatment Arm	Visit	Day	ECG Timepoint	ECG Type
All	Screening	-21 to -1	Anytime	12-lead

POL6326-009	X 7••4	D		
Ireatment	VISIT	Day	ECG Timepoint	ECG
Arm				Туре
Balixafortide +	Cycle 1	1	Within 1 hour prior to administration	Duplicate
eribulin			of balixafortide	12-lead
Balixafortide +	Cycle 1	2	Immediately before starting the	12-lead
eribulin			balixafortide infusion	
Eribulin	Cycle 1	2	Immediately before starting the	12-lead
monotherapy	5		eribulin infusion	
mono monopy				
All	Cycle 1	2	Within 1 hour after completing the	12-lead
		_	eribulin infusion	
Balivafortida +	Cycle 1	0	Immediately before starting the	12-lead
	Cycle I	,	halingfactide infraing	12-10au
eribulin			balixatoride infusion	
E siles l'a	Cruele 1	0	Turner list las la fama starting die	12 land
Eribulin	Cycle I	9	immediately before starting the	12-lead
monotherapy			eribulin infusion	
	~ 1 4			10.1.1
All	Cycle I	9	Within 1 hour after completing the	12-lead
			eribulin infusion	
Balixafortide +	Cycle 2 &	2	Immediately before starting the	12-lead
eribulin	subsequent		balixafortide infusion	
	cycles ^a			
	-			
Eribulin	Cycle 2 &	2	Immediately before starting the	12-lead
monotherapy	subsequent		eribulin infusion	
17	cvcles ^a			
	5			
All	Cycle 2 &	2	Within 1 hour after completing the	12-lead
	subsequent	_	eribulin infusion	
	cycles ^a			
	eyeres			
Balixafortide +	Cycle 2 &	9	Immediately before starting the	12-lead
aribulin	cycle 2 &	,	halivafartida infusion	12 1000
eribuilli	subsequent			
	cycles			
Enilari.	Cruele 2 P	0	In market the bafana starting the	12 land
Eribulin	Cycle 2α	9	immediately before starting the	12-lead
monotherapy	subsequent		eribulin infusion	
	cycles ^a			
4 11	a 1 a -			10.1
All	Cycle 2 &	9	Within 1 hour after completing the	12-lead
	subsequent		eribulin infusion	
	cycles ^a			
All	EoT	-	Anytime	12-lead

a: After Cycle 2, the frequency of ECG recordings can be reduced to every 2 cycles if deemed clinically appropriate (i.e. absence of ECG findings in earlier assessments).

ECG measurements include Ventricular rate, PR interval, QT interval, QTcF interval, RR interval, and QRS duration. Summary tables of ECG results will be presented and changes from baseline will be summarized by treatment arm and by cycle, by day and by ECG timepoint. Any clinically significant changes will be recorded as AEs.

QTcF intervals between >480 ms and \leq 500 ms (Grade 2) or between >500 ms or <600 ms (Grade 3) will be identified and summarized by study treatment arm, by cycle, by day and by ECG timepoint.

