9.2.6.2 QT Prolongation

In the event of a QT prolongation, possible alternative reversible causes such as serum electrolyte abnormalities, or concomitant medications with the potential to prolong the QT interval (Appendix 1 Prohibited Medications) should be evaluated. If such reversible causes are identified, they should be corrected accordingly (i.e. correction of electrolyte abnormalities with supplements to within normal limits and/or discontinuation of concomitant medications known to prolong the QT interval).

At the first occurrence of a QTc interval >480 msec and ≤500 msec (Grade 2), Investigators should identify and treat alternative reversible causes and initiate more frequent ECG monitoring according to the Investigator's best medical judgement until QTc ≤480 msec. Dosing of the study drug can continue. However, if the QTc interval remains >480 msec or reoccurs in the absence of alternative causes or despite their correction, specialist cardiologist consultation should be arranged, and treatment continuation discussed with the cardiologist and Medical Monitor.

If at any time the mean QTcF is prolonged (≥501 msec on at least two separate ECGs, [i.e. CTCAE Grade ≥3]), then the ECGs should be re-evaluated by a qualified person at the site for confirmation as soon as the finding is made, including verification that the machine reading is accurate. If manual reading confirms a QTc of ≥501 msec, immediate search for reversible causes (including electrolyte abnormalities, and concomitant medications for drugs with the potential to prolong the QT interval [see Appendix 1 Prohibited Medications]) must be performed.

If QTc interval reverts to <501 msec, and, in the judgment of the Investigator(s) in consultation with the Sponsor, the cause is determined to be due to cause(s) other than study drugs, treatment may be continued with appropriate ECG monitoring.

If a prolonged QTcF interval >501 msec is confirmed, study drug will be held until the QTc interval decreases to <501 msec.

Prior to concluding that an episode of prolongation of the QTc interval is due to study drug, thorough consideration should be given to potential precipitating factors (e.g. change in patient clinical condition, effect of concurrent medication, electrolyte disturbance) and possible evaluation by a specialist.

Protocol No.: POL6326-009

Version 3.0

Events of QT prolongation >480 msec, or otherwise considered clinically significant, must be reported as AEs.

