Eribulin monotherapy	Cycle 2 & subsequent cycles ^a	2	Immediately before starting the eribulin infusion	12-lead
All	Cycle 2 & subsequent cycles ^a	2	Within 1 hour after completing the eribulin infusion	12-lead
Balixafortide + eribulin	Cycle 2 & subsequent cycles ^a	9	Immediately before starting the balixafortide infusion	12-lead
Eribulin monotherapy	Cycle 2 & subsequent cycles ^a	9	Immediately before starting the eribulin infusion	12-lead
All	Cycle 2 & subsequent cycles ^a	9	Within 1 hour after completing the eribulin infusion	12-lead
All	EoT	-	Anytime	12-lead

Protocol No.: POL6326-009

Version 3.0

a: After Cycle 2, the frequency of ECG recordings can be reduced to every 2 cycles if deemed clinically appropriate (i.e. absence of ECG findings in earlier assessments).

Additional ECGs can be performed as clinically indicated at any time and the results recorded in the source data and eCRF.

All ECGs will be performed using a 12-lead (with a 10-second rhythm strip) tracing. ECG measurements will include PR interval, QT interval, QTcF interval, RR interval, and QRS complex. It is preferable that the machine used has a capacity to calculate the standard intervals automatically.

ECG interval readings by the ECG recorder's algorithm will be read and interpreted at the investigational site for eligibility determination and patient safety monitoring and documentation stored in the source documents.

Patients should be supinely resting for at least 10 minutes before and 5 minutes after timepoints for ECG recordings. When the timing of the ECG coincides with blood collection, the ECG should be obtained first. During treatment, ECGs will be compared to Screening or most recent ECG and any clinically significant changes will be recorded as AEs and evaluated further, as clinically warranted. Episodes of QT prolongation should be managed as described in Section 9.2.6.2.

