12.4.4 Physical Examination

A summary table for the shift from baseline to post-baseline timepoints for physical examination will be provided for the Safety population. All physical examination results will be presented in a data listing.

12.4.5 12-Lead Electrocardiogram

ECG data will be summarized by study medication arm and by cycle using descriptive statistics for change-from-baseline values and categorical outliers. Any clinically significant changes will be recorded as AEs.

QTc intervals between >480 msec and ≤500 msec (Grade 2) and or between ≥501 msec from baseline (Grade 3) will be identified and summarized by study medication arm.

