4.5. Mapping of Unscheduled visits

All planned assessments will be reported without any remapping.

Missing scheduled assessments will not be replaced by unscheduled assessments.

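### After Cycle 2, ECGs may be thinned only in patients without earlier findings, so SAP 9.5's by-cycle QTcF tables describe a selected group in skipped cycles, and no per-patient worst-value table is planned

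*SAP*

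**What the plan says.** Protocol 9.8 (Table 11) schedules ECGs on fixed days and timepoints for all patients in Cycles 1 and 2. After that, footnote a to the table says the recording frequency "can be reduced to every 2 cycles if deemed clinically appropriate (i.e. absence of ECG findings in earlier assessments". SAP 9.5 repeats the footnote. Reduction is optional, the rule is the same in both arms, and neither document defines an ECG finding.

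SAP 9.5 then plans two displays. For the ECG measurements, "changes from baseline will be summarized by treatment arm and by cycle, by day and by ECG timepoint". QTcF values in the Grade 2 and Grade 3 ranges "will be identified and summarized by study treatment arm, by cycle, by day and by ECG timepoint". Protocol 12.4.5 says "ECG data will be summarized by study medication arm and by cycle using descriptive statistics for change-from-baseline values and categorical outliers", and that the two QTc grade categories "will be identified and summarized by study medication arm", without naming cycle. The SAP adds the split by cycle, day and timepoint and does not keep an overall count.

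On unscheduled tracings, SAP 4.5 says: "Missing scheduled assessments will not be replaced by unscheduled assessments". Protocol 9.2.6.2 tells investigators, at a first QTc above 480 and up to 500 msec, to "initiate more frequent ECG monitoring according to the Investigator's best medical judgement".

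**The concern.** Whether a patient has an ECG in a given cycle after Cycle 2 depends on that patient's earlier ECGs. Patients with findings remain on every-cycle recording, while patients without may miss alternate cycles. A by-cycle mean uses whoever was recorded, so in a skipped cycle it leans towards patients with findings. Nothing in SAP 9.5 deals with ECGs skipped by design.

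Extra tracings taken because QTc was long have no cell in a table indexed by scheduled day and timepoint. SAP 9.5 also has no row or table that collapses over cycles, although the SAP provides one elsewhere: laboratory results are summarised overall as well as by cycle (9.2), and medication errors by visit and overall (9.6.1).

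QTc prolongation is an adverse event of particular interest. A reader of the ECG tables will want to know how many patients per arm ever exceeded 480 or 500 ms and how large each patient's maximum change was. The planned tables do not answer either question, and the by-cycle means they do give are hard to interpret after Cycle 2.

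**Working it through.** The documents state no QTcF mean, standard deviation, outlier rate, finding rate or uptake of thinning. There is no plan figure to reproduce, and every size below is illustrative.

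**1. Simple mixture (assumed values).** Let 10% of patients have findings with mean change +30 ms, and the rest +5 ms.
- Everyone recorded: 0.10 × 30 + 0.90 × 5 = +7.5 ms.
- Half of the finding-free patients skip: (0.10 × 30 + 0.45 × 5) / 0.55 = 5.25 / 0.55 = +9.5 ms.
- All finding-free patients skip: +30 ms.

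Suppose 2% of all patients exceed 480 ms and all of them are in the finding group. With full thinning the share among recorded patients is 0.02 / 0.10 = 20%. On a whole-group denominator it stays at 2%.

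**2. Which denominator the SAP uses.** SAP section 4 (General Statistical Considerations) sets the percentage denominator as the patients in the analysis set unless otherwise noted. SAP 9.5 notes no exception. SAP 9.2 does make one, for laboratory shift tables, which use available data per cycle and day. So the plan as written divides QTcF outliers by the whole set, and an unrecorded patient counts as a non-outlier.

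**3. Simulation.** I used 400,000 patients with no time trend. Assumptions: true QTcF mean 425 ms, between-patient SD 18, mean change +5 ms with patient SD 8 or 12, within-patient SD 10, and eight ECGs in Cycles 1–2. All thinned patients skip the same cycle. The share on treatment at Cycle 4 is 0.5^((3 × 21 / 30.4375) / 3.9) = 0.69, using the 3.9-month median PFS assumed for eribulin in SAP 4.1 as a stand-in. Results for a skipped cycle at 50 / 80 / 100% uptake among finding-free patients:

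| Patient SD; definition of finding (share with it) | Mean change, ms | >480 ms, % of those recorded | >480 ms, % of analysis set |
|---|---|---|---|
| 8; any >450 ms (38.9%) | 5.8 / 6.9 / 8.0 | 1.70 / 2.31 / 3.03 | 0.82 / 0.82 / 0.82 |
| 8; any >480 ms (4.1%) | 5.3 / 5.9 / 11.6 | 2.05 / 4.31 / 22.97 | 0.74 / 0.69 / 0.66 |
| 8; change >30 ms (19.0%) | 7.1 / 10.6 / 18.0 | 1.37 / 1.71 / 2.40 | 0.57 / 0.42 / 0.32 |
| 12; any >450 ms (39.9%) | 6.7 / 8.8 / 11.1 | 2.55 / 3.45 / 4.49 | 1.23 / 1.23 / 1.23 |
| 12; any >480 ms (5.6%) | 5.6 / 7.3 / 17.8 | 3.12 / 6.39 / 26.87 | 1.14 / 1.08 / 1.04 |
| 12; change >30 ms (23.8%) | 8.1 / 12.9 / 21.4 | 2.31 / 3.09 / 4.53 | 0.99 / 0.84 / 0.75 |

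In a cycle where everyone on treatment is recorded, mean change is +5.0 ms. The >480 ms share is then 1.18% (SD 8) or 1.79% (SD 12) of those recorded, and 0.82% or 1.23% of the analysis set.

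The skipped-cycle mean is therefore shifted upward in every scenario. The outlier percentage on the SAP default denominator is equal or lower in every scenario. Drug holds are not modelled.

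**The case against.** Several points limit the concern.

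- A thinned patient is still recorded every second cycle, and nothing says all patients skip the same one. Where everyone is recorded, this mechanism adds nothing; if skipping is staggered, the effect is diluted. A reader might infer a steady upward drift after Cycle 2, but the documents do not support that. **Stands.**
- A reader might also infer that outlier rates rise in skipped cycles. That needs patients with an ECG as the denominator, which is not the SAP default. **Stands**, although the default has its own fault: it dilutes the rate by counting unrecorded patients as normal.
- It is tempting to say that the highest values, caught on unscheduled tracings, reach no summary. They do reach one. Protocol 9.2.6.2 requires QT prolongation above 480 msec to be reported as an adverse event. SAP 9.1.8 summarises QTc prolongation as an event of particular interest by arm, with a Kaplan-Meier time to onset, and SAP section 9 lists all safety data. **Stands**, but these are investigator-identified events. They do not give the maximum QTcF or maximum change in ms.
- A finding need not be a QTc finding, since PR, RR and QRS are also measured. For other findings the shift may be nil. Protocol 9.2.6.2 also holds study drug at a confirmed QTcF of 501 msec or more, which pulls later values down. **Stands**: the net direction is not certain.
- The thinning rule is the same in both arms and the tables are descriptive. A between-arm distortion requires different finding rates or different uptake. That is possible in an open-label trial but is not shown. **Stands.**
- SAP section 4 already displays the number of missing observations, so a fall in recorded patients would be visible. This helps, but it does not say who is missing.
- A per-patient maximum rises with the number of tracings, so it carries informative sampling of its own. **Stands**, and the fix has to allow for it.

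**Conclusion.** The point holds in a limited form. After Cycle 2, mean QTcF and mean change in cycles skipped by thinned patients come from an outcome-selected group. They tend to be shifted upward when the findings concern QTc. The size cannot be derived from the documents. Under the stated assumptions the mean change was +5.3 to +21.4 ms against a true +5.0 ms, and the upper end needed full uptake with everyone skipping the same cycle.

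Outlier percentages on the SAP default denominator are diluted or unchanged in those cycles: 0.32% to 1.23%, against 0.82% to 1.23% when all on treatment are recorded. The ECG section gives no per-patient worst QTcF, no maximum change, and no count per arm of patients ever measured above 480 or 500 ms.

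The documents do not support a general later-cycle rise, inflated outlier rates, a total loss of the high values, or a demonstrated between-arm bias. The conclusion rests on the thinning option being used to some extent and on SAP 9.5 being applied as written.

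**What to change.** Change SAP 9.5 in two ways.

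1. Make the main QTcF table a per-patient one by arm: worst post-baseline QTcF category and maximum change from baseline, using scheduled and unscheduled ECGs. The denominator is patients with at least one post-baseline ECG. Add a version restricted to scheduled Cycle 1–2 ECGs, where the schedule is the same for all patients within an arm. By Table 11 and the SAP's safety baseline rule, that schedule gives 4 + 4 = 8 post-baseline tracings in the combination arm and 3 + 4 = 7 in the eribulin arm, whose first Day 2 pre-dose tracing is baseline. Note this difference under the table.
2. Limit by-cycle means and outlier tables to Cycles 1–2. After that use two-cycle blocks (3–4, 5–6, and so on) with one pre-specified scheduled value per patient, for example the first scheduled ECG in the block at each timepoint. Show the number with an ECG and use it as the percentage denominator. A patient who leaves treatment before the recorded cycle of a block still drops out of it, so the blocks reduce the selection rather than remove it entirely.

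The cost is SAP wording and one or two tables from data already collected, and less by-cycle detail after Cycle 2. No change to ECG monitoring is proposed.
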